1.1 Purpose

To establish standards that will ensure that a Dana-Farber/Harvard Cancer Center Multi-Center protocol will comply with Federal Regulations, Health Insurance Portability and Accountability Act (HIPAA) requirements and applicable DF/HCC Policies and Operations .

2. GENERAL ROLES AND RESPONSIBILITIES

For DF/HCC Multi-Center Protocols, the following general responsibilities apply, in addition to those outlined in DF/HCC Policies for Sponsor-Investigators:

2.1 Coordinating Center

The general responsibilities of the Coordinating Center may include but are not limited to:

- Assist in protocol development.
- Maintain FDA correspondence, as applicable.
- Review registration materials for eligibility and register participants from External Sites in the DF/HCC clinical trial management system (CTMS).
- Distribute protocol and informed consent document updates to External Sites as needed.
- Oversee the data collection process from External Sites.
- Maintain documentation of Serious Adverse Event (SAE) reports and deviations/violation submitted by Participating Institutions and provide to the DF/HCC Sponsor for timely review and submission to the DFCI IRB, as necessary.
- Distribute serious adverse events reported to the DF/HCC Sponsor that fall under the DFCI IRB Adverse Event Reporting Policy to all External Site.
- Provide External Site with information regarding DF/HCC requirements that they will be expected to comply with.
- Carry out plan to monitor External Site either by on-site or remote monitoring.
- Maintain Regulatory documents of all External Sites which includes but is not limited to the following: local IRB approvals/notifications from all External Sites, confirmation of Federalwide Assurances (FWAs) for all sites, all SAE submissions, Screening Logs for all sites, IRB approved consents for all sites
- Conduct regular communications with all External Sites (conference calls, emails, etc) and maintain documentation all relevant communications.

2.3 External Site

An External Site is an institution that is outside the DF/HCC and DF/PCC consortium that is collaborating with DF/HCC on a protocol where the sponsor is a DF/HCC investigator. The External Site acknowledges the DF/HCC Sponsor as having the ultimate authority and responsibility for the overall conduct of the study.

Each External Site is expected to comply with all applicable federal regulations and DF/HCC requirements, the protocol and HIPAA requirements.

The general responsibilities for each Externals may include but are not limited to:

- Document the delegation of research specific activities to study personnel.
Commit to the accrual of participants to the protocol.
- Submit protocol and/or amendments to their local IRB of record.
Maintain regulatory files as per sponsor requirements.
- Provide the Coordinating Center with regulatory documents or source documents as requested.
- Participate in protocol training prior to enrolling participants and throughout the trial as required (i.e. teleconferences).
- Update Coordinating Center with research staff changes on a timely basis.
- Register participants through the Coordinating Center prior to beginning research related activities.
- Submit Serious Adverse Event (SAE) reports to local IRB per institutional requirements and to the Coordinating Center, in accordance with DF/HCC requirements.
- Submit protocol deviations and violations to local IRB per institutional requirements and to the DF/HCC Sponsor in accordance with DF/HCC requirements.
- Order, store and dispense investigational agents and/or other protocol mandated drugs per federal guidelines and protocol requirements.
- Have office space, office equipment, and internet access that meet HIPAA standards.
- Participate in any quality assurance activities and meet with monitors or auditors at the conclusion of a visit to review findings.
- Promptly provide follow-up and/or corrective action plans for any monitoring queries or audit findings.

3. DF/HCC REQUIREMENTS FOR MULTI-CENTER PROTOCOLS

Certain DF/HCC Policy requirements apply to External Sites participating in DF/HCC research. The following section will clarify DF/HCC requirements and further detail the expectations for participating in a DF/HCC Multi-Center protocol.

3.1 Protocol Revisions and Closures

The External Sites will receive notification of protocol revisions and closures from the Coordinating Center. When under a separate IRB, it is the individual External Site's responsibility to notify its IRB of these revisions.

- **Protocol revisions:** External Sites will receive written notification of protocol revisions from the Coordinating Center. All protocol revisions should be IRB approved and

implemented within a timely manner from receipt of the notification

- **Protocol closures and temporary holds:** External Sites will receive notification of protocol closures and temporary holds from the Coordinating Center. Closures and holds will be effective immediately. In addition, the Coordinating Center, will update the External Sites on an ongoing basis about protocol accrual data so that they will be aware of imminent protocol closures.

3.2 Informed Consent Requirements

The DF/HCC approved informed consent document will serve as a template for the informed consent for External Site. The External Site consent form must follow the consent template as closely as possible and should adhere to specifications outlined in the DF/HCC Guidance Document on Model Consent Language for Investigator-Sponsored Multi-Center Trials. This document will be provided separately to each External Site upon request.

External Sites must send their version of the informed consent document to the Coordinating Center for sponsor review and approval. If the HIPAA authorization is a separate document, please submit to the sponsor for the study record. Once sponsor approval is obtained, the External site may submit to their IRB of record, as applicable. In these cases, the approved consent form must also be submitted to the Coordinating Center after approval by the local IRB for all consent versions.

The Principal Investigator (PI) at each External Site will identify the appropriate members of the study team who will be obtaining consent and signing the consent form for protocols. External Sites must follow the DF/HCC requirement that for all interventional drug, biologic, or device research, only attending physicians may obtain initial informed consent and any re-consent that requires a full revised consent form.

3.3 IRB Re-Approval

Verification of IRB re-approval for the External Sites is required in order to continue research activities. There is no grace period for continuing approvals.

The Coordinating Center will not register participants if a re-approval letter is not received from the External Site on or before the anniversary of the previous approval date.

3.4 DF/HCC Multi-Center Protocol Confidentiality

All documents, investigative reports, or information relating to the participant are strictly confidential. Whenever reasonably feasible, any participant specific reports (i.e. Pathology Reports, MRI Reports, Operative Reports, etc.) submitted to the Coordinating Center should be de-identified. It is recommended that the assigned protocol case number be used for all participant specific documents. Participant initials may be included or retained for cross verification of identification.

3.5 Participant Registration and Randomization

To register a participant, the following documents should be completed by the External Site and faxed or e-mailed to the Coordinating Center:

- Current IRB approved informed consent document informed consent document signed by participant and investigator. Participant name and MRN must be redacted. Please ensure the participant's initials are written on each page of the informed consent document.
- HIPAA authorization form (if separate from the informed consent document)
- Signed and dated Eligibility Checklist.
- External site subject registration form
- The following source documentation is typically required:
 - Documentation of prior treatments/procedures performed to treat RCC
 - Reports documenting disease status
 - MRI or CT Brain
 - Chest CT
 - CT or MRI Abdomen and Pelvis
 - Bone Scan if applicable
 - Pathology Report
 - Concomitant medication list
 - Progress note or equivalent documentation of consenting visit
 - Progress note documenting medical history and oncologic history
 - Screening Labs
 - Screening visit note with vital signs, weight, height, ECOG performance status, physical examination
 - Screening ECG, ECHO

The Coordinating Center will review the submitted documents in order to verify eligibility and consent. To complete the registration process, the Coordinating Center will:

- Register the participant on the study with the DF/HCC Clinical Trial Management System (CTMS).
- Upon receiving confirmation of registration, the Coordinating Center will inform the External Site and provide the study specific participant case number, and, if applicable, assigned treatment and/or dose level.

At the time of registration, the following identifiers are required for all subjects: initials, date of birth, gender, race and ethnicity. Once eligibility has been established and the participant successfully registered, the participant is assigned a unique protocol case number. External Sites should submit all de-identified subsequent communication and documents to the Coordinating Center, using this case number to identify the subject.

3.6 Initiation of Therapy

Participants must be registered with the DF/HCC CTMS before the initiation of treatment or other protocol-specific interventions. Treatment and other protocol-specific interventions may not be initiated until the External Site receives confirmation of the participant's registration from the

Coordinating Center. The DF/HCC Sponsor and DFCI IRB must be notified of any violations to this policy.

3.7 Eligibility Exceptions

No exceptions to the eligibility requirements for a protocol without IRB approval will be permitted. All External Sites are required to fully comply with this requirement. The process for requesting an eligibility exception is defined below.

3.8 Data Management

DF/HCC develops case report forms (CRF/eCRFs), for use with the protocol. These forms are designed to collect data for each study. DF/HCC provides a web based training for all eCRF users.

3.8.1 Data Forms Review

Data submissions are monitored for timeliness and completeness of submission. If study forms are received with missing or questionable data, the submitting institution will receive a written or electronic query from the DF/HCC Office of Data Quality, Coordinating Center, or designee.

Responses to all queries should be completed and submitted within 14 calendar days.

If study forms are not submitted on schedule, the External Sites will periodically receive a Missing Form Report from the Coordinating Center noting the missing forms.

3.9 Protocol Reporting Requirements

Federal Regulations require an IRB to review proposed changes in a research activity to ensure that researchers do not initiate changes in approved research without IRB review and approval, except when necessary to eliminate apparent immediate hazards to the participant. DF/HCC requires all departures from the defined procedures set forth in the IRB approved protocol to be reported to the DF/HCC Sponsor, who in turn is responsible for reporting to the DFCI IRB.

3.9.1 Definitions

Protocol Deviation: Any departure from the defined procedures set forth in the IRB-approved protocol which is *prospectively approved* prior to its implementation.

Protocol Exception: Any protocol deviation that relates to the eligibility criteria, e.g. enrollment of a participant who does not meet all inclusion/exclusion criteria.

Protocol Violation: Any protocol departure that was not *prospectively approved* by the IRB prior to its initiation or implementation.

3.9.2 Protocol Deviations, Exceptions and Violations

Federal Regulations require an IRB to review proposed changes in a research activity to ensure that researchers do not initiate changes in approved research without IRB review and approval, except when necessary to eliminate apparent immediate hazards to the participant. DF/HCC requires all departures from the defined procedures set forth in the IRB approved protocol to be reported to the DF/HCC Sponsor and to the IRB of record.

3.9.3 Reporting Procedures

Requests to deviate from the protocol require approval from the IRB of record and the sponsor.

All protocol violations must be sent to the Coordinating Center in a timely manner. The Coordinating Center will provide training for the requirements for the reporting of violations.

3.9.4 Guidelines for Reporting Serious Adverse Events

Guidelines for reporting Adverse Events (AEs) and Serious Adverse Events (SAEs) are detailed in protocol section 7.

External Sites must report the SAEs to the DF/HCC Sponsor and the Coordinating Center following the DFCI IRB Adverse Event Reporting Policy.

The Coordinating Center will maintain documentation of all External Site Adverse Event reports and be responsible for communicating to all participating investigators, any observations reportable under the DFCI IRB Reporting Requirements. External Sites will review and submit to their IRB according to their institutional policies and procedures

3.9.5 Guidelines for Processing IND Safety Reports

The DF/HCC Sponsor will review all IND Safety Reports per DF/HCC requirements, and ensure that all IND Safety Reports are distributed to the External Sites as required by DF/HCC Policy. External Sites will review/submit to the IRB according to their institutional policies and procedures.

4. MONITORING: QUALITY CONTROL

The quality control process for a clinical trial requires verification of protocol compliance and data accuracy. The Coordinating Center, with the aid of the DF/HCC Office of Data Quality, provides quality control oversight for the protocol.

4.1 Ongoing Monitoring of Protocol Compliance

The External Sites may be required to submit participant source documents to the Coordinating Center for monitoring. External Sites may also be subject to on-site monitoring conducted by the Coordinating Center.

The Coordinating Center will implement ongoing monitoring activities to ensure that External Sites are complying with regulatory and protocol requirements, data quality, and participant safety. Monitoring practices may include but are not limited to source data verification, and review and analysis of eligibility requirements, informed consent procedures, adverse events and all associated documentation, review of study drug administration/treatment, regulatory files, protocol departures reporting, pharmacy records, response assessments, and data management

Site visits will generally occur once a year for sites that are actively enrolling participants and have participants in treatment. Additional monitoring activities may occur if incidences of non-compliance are discovered or at the request of the DF/HCC Sponsor. Virtual monitoring (source documents are sent to DFCI for review) may be performed in lieu of a site visit if the study staff and PI determine that virtual monitoring is appropriate for the site. The decision to perform virtual monitoring in lieu of a site visit will be based upon the site's enrollment, study compliance history, history collaborating with DFCI on other multi-center studies, and number of participants in active treatment.

Monitoring will occur before the clinical phase of the protocol begins and will continue during protocol performance through study completion.

Teleconferences between DFCI and the participating sites will be conducted on approximately a monthly basis. Meeting minutes for teleconferences will be issued to all participating sites. Site initiation visits will be conducted via teleconference. Ongoing training will also be conducted via teleconference as needed. The Coordinating Center, Dana Farber Cancer Institute will be available to all participating sites for resolving questions, concerns and facilitating compliance.

4.2 Monitoring Reports

The DF/HCC Sponsor will review all monitoring reports to ensure protocol compliance. The DF/HCC Sponsor may increase the monitoring activities at External Sites that are unable to comply with the protocol, DF/HCC Sponsor requirements or federal and local regulations.

4.3 Accrual Monitoring

Prior to extending a protocol to an external site, the DF/HCC Sponsor will establish accrual requirements for each external site. Accrual will be monitored for each external site by the DF/HCC Sponsor or designee. Sites that are not meeting their accrual expectations may be subject to termination.

The following **minimum** accrual requirements are recommended:

- 1) Phase I: 2 per site/annually
- 2) Phase II-III: 3 per site/annually. However, given the additional regulatory burden and cost of overseeing each site, a consideration of 5 per site/annually should be a minimum target for each site.
- 3) Note: Diseases that are extremely rare may have accrual expectations of 0-1 accruals/year.]

5. AUDITING: QUALITY ASSURANCE

Auditing is a method of Quality Assurance and involves the systematic and independent examination of all trial related activities and documents. Audits determine if evaluated activities were appropriately conducted and whether data was generated, recorded and analyzed, and accurately reported per the protocol, applicable Policies, and the Code of Federal Regulations (CFR).

5.1 DF/HCC Internal Audits

All External Sites are subject to audit by the DF/HCC Office of Data Quality (ODQ). Typically, approximately 3-4 participants would be audited at the site over a 2-day period. If violations which impact participant safety, or the integrity of the study are found, more participant records may be audited.

5.2 Audit Notifications

It is the External Site's responsibility to notify the Coordinating Center of all external audits or inspections (e.g., FDA, EMA, NCI) that involve this protocol. All institutions will forward a copy of final audit and/or re-audit reports and corrective action plans (if applicable) to the Coordinating Center, within 12 weeks after the audit date.

5.3 Audit Reports

The DF/HCC Sponsor will review all final audit reports and corrective action plans, if applicable. The Coordinating Center, must forward any reports to the DF/HCC ODQ per DF/HCC policy for review by the DF/HCC Audit Committee. For unacceptable audits, the DF/HCC Audit Committee would forward the final audit report and corrective action plan to the DFCI IRB as applicable.

5.4 External Site Performance

The DF/HCC Sponsor and the IRB of record are charged with considering the totality of an institution's performance in considering institutional participation in the protocol.

External Sites that fail to meet the performance goals of accrual, submission of timely and accurate data, adherence to protocol requirements, and compliance with state and federal regulations, may be put on hold or closed.

APPENDIX D FKSI-19

STUDY ID _____

STUDY NUMBER _____

DATE _____

Below is a list of statements that other people with your illness have said are important. **Please circle or mark one number per line to indicate your response as it applies to the past 7 days.**

		Not at all	A little bit	Some-what	Quite a bit	Very much
GP1	I have a lack of energy	0	1	2	3	4
GP4	I have pain	0	1	2	3	4
C2	I am losing weight	0	1	2	3	4
HI7	I feel fatigued	0	1	2	3	4
B1	I have been short of breath	0	1	2	3	4
BRM3	I am bothered by fevers (episodes of high body temperature)	0	1	2	3	4
BP1	I have bone pain	0	1	2	3	4
L2	I have been coughing	0	1	2	3	4
HI12	I feel weak all over	0	1	2	3	4
RCC 2	I have had blood in my urine	0	1	2	3	4
C6	I have a good appetite	0	1	2	3	4
GF5	I am sleeping well	0	1	2	3	4
GE6	I worry that my condition will get worse	0	1	2	3	4
GP2	I have nausea	0	1	2	3	4
C5	I have diarrhea (diarrhoea)	0	1	2	3	4
GP5	I am bothered by side effects of treatment	0	1	2	3	4
GF1	I am able to work (include work at home)	0	1	2	3	4

GF3	I am able to enjoy life	0	1	2	3	4
GF7	I am content with the quality of my life right now	0	1	2	3	4

DRS-P = Disease-related symptoms subscale – Physical

DRS-E = Disease-related symptoms subscale – Emotional

TSE = Treatment side effects subscale

FWB = Function and well-being subscale

APPENDIX E BRIEF FATIGUE INVENTORY

Brief Fatigue Inventory

STUDY ID# _____ HOSPITAL # _____

Date: _____ / _____ / _____ Time: _____

Name: _____ Last _____ First _____ Middle Initial _____

Throughout our lives, most of us have times when we feel very tired or fatigued. Have you felt unusually tired or fatigued in the last week? Yes No

1. Please rate your fatigue (weariness, tiredness) by circling the one number that best describes your fatigue right NOW.

0	1	2	3	4	5	6	7	8	9	10
No Fatigue	As bad as you can imagine									

2. Please rate your fatigue (weariness, tiredness) by circling the one number that best describes your USUAL level of fatigue during past 24 hours.

0	1	2	3	4	5	6	7	8	9	10
No Fatigue	As bad as you can imagine									

3. Please rate your fatigue (weariness, tiredness) by circling the one number that best describes your WORST level of fatigue during past 24 hours.

0	1	2	3	4	5	6	7	8	9	10
No Fatigue	As bad as you can imagine									

4. Circle the one number that describes how, during the past 24 hours, fatigue has interfered with your:

A. General activity
0 1 2 3 4 5 6 7 8 9 10
Does not interfere Completely Interferes

B. Mood
0 1 2 3 4 5 6 7 8 9 10
Does not interfere Completely Interferes

C. Walking ability
0 1 2 3 4 5 6 7 8 9 10
Does not interfere Completely Interferes

D. Normal work (includes both work outside the home and daily chores)
0 1 2 3 4 5 6 7 8 9 10
Does not interfere Completely Interferes

E. Relations with other people
0 1 2 3 4 5 6 7 8 9 10
Does not interfere Completely Interferes

F. Enjoyment of life
0 1 2 3 4 5 6 7 8 9 10
Does not interfere Completely Interferes

Copyright 1997
The University of Texas M. D. Anderson Cancer Center
All rights reserved.

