3.2 Exclusion Criteria

A patient will be excluded from the study if he or she meets any of the following criteria:

- 3.2.1 Patients receiving any other investigational agents.
- 3.2.2 Patients who received prior CDK4/6 inhibitors.
- 3.2.3 For Arm 2 only, patients who have received prior HIF-2 α inhibitor.
- 3.2.4 Participants who have received any continuous or intermittent small molecule therapeutics (excluding monoclonal antibodies) \leq 4 effective half-lives prior to starting study drug or who have not recovered from side effects of such therapy to grade 1 or less (except for non-clinically significant laboratory abnormalities).
- 3.2.5 Patients must have discontinued all biologic therapy including therapeutic antibodies at least 28 days before C1D1.
- 3.2.6 Participants who have received wide field radiotherapy \leq 4 weeks or limited field radiation for palliation \leq 2 weeks prior to starting study drug or who have not recovered from side effects of such therapy to at least grade 1.
- 3.2.7 Participants with untreated metastatic ccRCC to the brain may participate in this trial if clinically and radiographically stable per investigator's assessment and not on corticosteroid (equivalent to $>/=$ 10 mg prednisone) or antiepileptic therapy.

- 3.2.8 O2 saturation <92% by arterial blood gas analysis or pulse oximetry on room air
- 3.2.9 Untreated deep vein thrombosis or pulmonary embolism, or event of deep vein thrombosis or pulmonary embolism within 2 weeks of treatment start. Patient should be on at least 1 week of anticoagulation before C1D1.
- 3.2.10 The patient has serious and/or uncontrolled preexisting medical condition(s) that, in the judgment of the investigator, would preclude participation in this study (for example, interstitial lung disease, severe dyspnea at rest or requiring oxygen therapy, severe renal impairment [e.g. estimated creatinine clearance <30ml/min], history of major surgical resection involving the stomach or small bowel, or preexisting Crohn's disease or ulcerative colitis or a preexisting chronic condition resulting in baseline Grade 2 or higher diarrhea)."

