5.2 Pre-Treatment Criteria

5.2.1 Cycle 1, Day 1

Patients should meet the clinical requirements for eligibility criteria at cycle 1 day 1. The following laboratory parameters should be met:

- ANC \geq 1,500 mcL
- platelet count \geq 100,000/uL
- hemoglobin \geq 10 g/dL (transfusions allowed)
- total bilirubin \leq 2.0 x institutional upper limit of normal with the following exception: patients with known Gilbert disease should have a serum bilirubin \leq 3 x ULN
- AST(SGOT)/ALT(SGPT) \leq 3 x institutional upper limit of normal with the following exception: patients with known liver metastases should have AST and ALT \leq 5 x ULN
- creatinine clearance \geq 30 mL/min/1.73 m² according to the Cockcroft-Gault formula

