1: Baseline evaluations are to be conducted within 28 days prior to the start of therapy, at the exception of the serum pregnancy test that must be performed within 7 days of therapy start. Scans must be done within 28 days prior to the start of therapy. All baseline screening should be done prior to registration.

2: A cycle will be defined as 28 days.

3: Imaging assessments, quality of life assessments will take place:

- every 8 weeks (+/- 7 days) for the first 6 months.

- After 6 months, imaging assessments and quality of life assessments can take place every 12 weeks (+/- 10 days)

4: Patients who discontinue from treatment will be asked to return to the clinic no more than 30 days after the last treatment for a treatment discontinuation visit. The visit at which a response assessment shows progressive disease may be used as the treatment discontinuation visit.

5: After progression/treatment discontinuation, participants will be followed for survival and receipt of next line therapies every 6 months until death or 2 years after treatment discontinuation. Participants removed from protocol therapy with ongoing treatment-related adverse event(s) will be followed until resolution or stabilization of the adverse event(s), initiation of new cancer-directed treatment, or death. Participants removed from protocol who did not experience disease progression will be followed as per protocol until progression, initiation of new cancer-directed treatment, or death.

6: Physical examination should include general description of participant, head, eyes, ears, nose, and throat, chest, abdominal, extremities, neurologic, skin, and lymph node examination. Any other evaluation is up to the discretion of the practitioner. It will not be considered a violation if the exam is not described as outlined here.

7: Vital signs include blood pressure, heart rate, respiratory rate, body temperature and pulse oximetry.

8: Hematology testing to include full CBC with WBC, ANC, hemoglobin, and platelet count and differential.

9: Serum chemistry to include full comprehensive metabolic panel with sodium, potassium, chloride, bicarbonate, BUN, creatinine, glucose, calcium, albumin, magnesium, and LDH.

10: Liver function tests to include AST, ALT, total bilirubin, and direct bilirubin

11: Coagulation factors to include PT, aPTT, and INR.

12: Pregnancy test only needs to be obtained in women of childbearing potential, within 7 days of therapy start.

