14.3.5 Quality of Life (QOL) Endpoints Analysis

The QOL will be measured by the Functional Assessment of Cancer Therapy-Kidney Symptom Index (FKSI)-19 and the Brief Fatigue Inventory (BFI). The questionnaires will be administered per schedule defined in section 11 (study calendar).

The FKSI-19 comprises of 19 items (each score ranging from 0-4) with a possible maximum total score of 76. The BFI is a 9 items questionnaire (each score ranging from 0-10) with a possible maximum score of 90. The calculated total scores at each timepoint and changes from baseline will be summarized with mean and standard deviation. Changes from baseline will be graphically presented. For FKSI-19, the proportion of patients with “clinically significant” symptoms (those scoring 3 or 4) will also be descriptively summarized over times across all items or by sub-domains. Missing assessments may be due to stopping treatment, not completing the FKSI or BFI assessments, and other reasons. Information on reasons why the patient did not complete the FKSI-19 or BFI Form will be collected.

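### Baseline BFI and FKSI-19 may be completed up to 28 days before first dose and are not repeated at Cycle 1 Day 1, so change from baseline can include an untreated month

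*Combined protocol and SAP*

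**What the plan says.** **Recall periods.** BFI item 1 (Appendix E) has the patient rate fatigue "by circling the one number that best describes your fatigue right NOW". Item 3 asks for the "WORST level of fatigue during past 24 hours", and items 2 and 4A–F use the same 24-hour period. The lead-in, "Have you felt unusually tired or fatigued in the last week", is a yes/no question and not one of the nine scored items. The FKSI-19 (Appendix D) covers the past 7 days.

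**Timing.** Table 15 in Section 11 places both forms in the pre-treatment column and every 8 weeks, with an end-of-treatment form also listed for the FKSI-19. Neither is listed at Cycle 1 Day 1, whereas ECOG status, vital signs, hematology, chemistry and adverse events are. Footnote 1 says "Baseline evaluations are to be conducted within 28 days prior to the start of therapy", shortens that window only for the pregnancy test, and adds "All baseline screening should be done prior to registration". Section 4.1 allows therapy to begin up to 7 calendar days after registration. Footnote 3 allows ±7 days around each 8-week assessment in the first 6 months.

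**Analysis.** Section 14.3.5 states that total scores at each timepoint and "changes from baseline will be summarized with mean and standard deviation". It has no rule on which pre-dose score is the baseline and no allowance for the interval before treatment.

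**The concern.** A form that asks about today or the past day describes the patient on the day it is completed. If that day is weeks before the first dose, the reference for treatment effect is a state that may have changed before treatment began.

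In this population the interval may not be neutral. Patients have failed, or could not tolerate, an anti-VEGFR drug and a checkpoint inhibitor (Section 3.1.2). Someone who completes the form while still on a prior small-molecule drug scores that drug's side effects, and later recovery could read as benefit of study drug or mask its toxicity. Untreated progression between form and first dose would push the other way and could read as toxicity.

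The affected items overlap with the expected toxicities in Section 7.1: fatigue is listed at 65% for abemaciclib and 67% for MK-6482, and diarrhea at 90% for abemaciclib. The arms are non-randomized and enrolled one after the other, so no concurrent control can subtract pre-dose drift.

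**Working it through.** The plan states no figure for this point, so there is none to reproduce. The check is a reading of the schedule plus date arithmetic.

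**1. Permitted gap.** From footnote 1 of Table 15, the interval from baseline form to first dose is 0 to 28 days. At the limit this is 28 ÷ 1 = 28 times the 24-hour BFI recall and 28 ÷ 7 = 4 times the FKSI-19 recall. These ratios show that the form's recall cannot reach forward to the first dose. They do not measure bias.

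**2. Is a Cycle 1 Day 1 form hidden by table extraction?** The columns of Table 15 are shifted in the text available. However, its separate column of data-capture timepoints also gives baseline and every 8 weeks (plus end of treatment for the FKSI-19), with no Cycle 1 Day 1 entry for either form.

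**3. Does other text shorten the window?** Section 12.1.3 asks for baseline evaluations close to the start of treatment, but it concerns tumor measurement and keeps the same 4-week limit. The 7 days from registration to therapy do not limit how long before registration the form was completed.

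**4. Share of the change interval that is untreated.** The first on-treatment form falls at day 56 ± 7, that is 49 to 63 days after first dose. With gap *b* and on-treatment time *f*, the share is *b* / (*b* + *f*).

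| Baseline form | *b* | *f* | *b* + *f* | Untreated share |
|---|---|---|---|---|
| Day 1, pre-dose | 0 | 56 | 56 | 0% |
| 7 days before | 7 | 56 | 63 | 11% |
| 28 days before, early form | 28 | 49 | 77 | 36% |
| 28 days before, nominal | 28 | 56 | 84 | 33% |
| 28 days before, late form | 28 | 63 | 91 | 31% |

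**5. How drift enters the result.** For each patient,

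Y(week 8) − Y(screening) = [Y(week 8) − Y(day 1)] + [Y(day 1) − Y(screening)].

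The second bracket precedes any study drug. Its mean passes into mean change one for one, and without a day-1 form it cannot be estimated or removed.

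**6. What may happen inside the gap.**
- Criterion 3.2.4 requires a prior small-molecule drug to have been stopped for more than "4 effective half-lives prior to starting study drug". The rule is tied to first dose, so stopping and recovery can fall after the form.
- Section 5.2.1 allows transfusion to meet the day-1 hemoglobin threshold.
- Nothing treats the disease between the end of prior therapy and day 1.

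Biologics differ: criterion 3.2.5 requires them to be stopped at least 28 days before Cycle 1 Day 1. The stop itself therefore cannot fall inside the window, though carry-over can.

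**The case against.** The strongest reply is that the schedule permits a gap but does not require one. A form completed the day before dosing complies, and nothing shows that early completion is expected. This stands: change from baseline *can* include pre-dose effects. A reader might infer that it always does, and the documents do not support that.

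A reader might also infer that the whole quality-of-life result depends on this form. It does not. Section 14.3.5 also summarizes total scores at each timepoint and, for the FKSI-19, the proportion with clinically significant symptoms over time. Neither subtracts baseline.

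A third tempting step is to express the drift in BFI points and compare it with sampling error. The documents give no standard deviation, expected shift or minimal important difference. They also describe the BFI on two scales: an item average in Section 14.1.2 and a total of up to 90 in Section 14.3.5. Recovery and decline can partly cancel in a mean, so not even the sign of a net shift is established.

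Residual toxicity is bounded in part, since criteria 3.2.4 and 3.2.6 require recovery to grade 1 from prior small-molecule therapy and radiation. But those limits apply at study entry and do not fix when the form is completed.

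Finally, the same 28-day limit applies to baseline scans, so the window is a consistent choice. That explains it, but a scan and a 24-hour symptom rating need not stay representative for equally long.

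**Conclusion.** The point holds as a minor one. The plan allows up to 28 untreated days in the change score, 28 of 84 nominal days (33%, or 31–36% across the visit window) to the first on-treatment form, and provides no measurement at first dose to isolate them. The 33% is the extreme of a permitted range that starts at 0. It assumes that the form is completed at the 28-day limit and week 8 is counted from first dose. The effect on scores cannot be derived in size or direction.

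Quality of life appears among the secondary endpoints in Section 14.1.2 but not among the objectives in Section 1, and its analysis is descriptive with no test. The response-rate endpoints, MTD determination, safety analysis and sample size are untouched.

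**What to change.** In Table 15, schedule the baseline FKSI-19 and BFI at Cycle 1 Day 1, completed before the first dose. A screening form, if kept, should serve only as a fallback when the day-1 form is missing. In Section 14.3.5, state that baseline is the last form completed before the first dose.

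The untreated part of the interval then falls to 0, and the first on-treatment form comes 49–63 days after baseline. This does not remove every pre-treatment influence: a patient transfused shortly before day 1, or still recovering from a prior drug, can continue to change afterward for reasons unrelated to study drug.

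The cost is one calendar change and one sentence in the analysis section. The visit already exists, Section 11 already requires assessments before any study agent, and a pre-dose blood sample is already drawn. The downside is a small risk of a missed form at a busy visit, which the fallback covers. No patients or visits are added.
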